Additional inclusion/exclusion criteria include the following: Eligible individuals must achieve a score of 4 or greater on the Auditory Verbal Comprehension Score, which is a subtest of the Western Aphasia Battery-Revised (WAB-R) for full enrollment/participation in the study. Eligible individuals must also name 1-146 of the 176 items correctly on the initial administration of the naming assessment for full enrollment/participation in the study. Individuals who name 0, or greater than 146 items will be excluded. These criteria will be assessed at the initial study visit, after informed consent has been obtained.

b. Source of subjects and recruitment methods

Individuals with aphasia will be recruited by referral from physicians, speech-language pathologists, and neuropsychologists. We will mail and email recruitment letters to neurologists and speech pathologists in the greater Boston area. Interested professionals will describe the study to the potential participants and ask them to contact the researcher if they are interested in participating in the experiment.

Individuals with aphasia will also be recruited from the MGH Institute of Health Professions Aphasia Center. SLPs will share study flyers with individuals with aphasia and ask if individuals are interested in meeting a member of the research team to learn more about the study. If they express interest, a member of the research team will be invited to come to the end of an upcoming scheduled therapy session to talk more about the study, or Aphasia Center staff can coordinate a meeting between the individual and a member of the study staff. It will be clearly communicated that the treating Speech language pathologist has no affiliation to the research study and that expressing or not expressing an interest to speak to research staff, in no way impacts the therapy services they receive in the MGH IHP Aphasia Center.

In addition, individuals with aphasia will be recruited via word of mouth, flyers, flyers/presentations at local aphasia centers, and emails to community health centers and via listservs (the American Speech-Language Hearing Association (ASHA) Special Interest Group 2 Neurogenic

Communication Disorders listserv, as well as the ASHA Special Interest Group 14 Cultural and Linguistic Diversity listserv). We will also recruit via Rally and the MGH IHP IRB-approved Recruitment Database.

IV. SUBJECT ENROLLMENT

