a. Methods of enrollment. We plan to enroll 20 individuals with aphasia in a single-subject design intervention study in which all participants receive the same intervention protocol.

b. Procedures for obtaining informed consent. Once interest in participating in the study is expressed, one of the co-investigators involved in this study will establish contact with potential participants over the phone or via email. The research project will be explained and interested persons will be invited to the research site to discuss the study. The purpose, procedures, possible benefits and risks of the study will be explained to all potential participants. Potential participants will also be instructed that they can withdraw from the experiment at any time.

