b. Study endpoints. The participant's participation with the study will end when they request to withdraw from the study, or after the post-treatment assessments have been completed, whichever occurs first.

c. Statistical methods.

We will use visual inspection⁶⁸, mixed-effects modeling, and effect size calculations to analyze all results. For visual inspection, we will use the conservative dual-criterion method^{20,27,82}. We will use mixed-effects modeling to estimate the extent to which treatment-specific factors (fixed effects), pre-treatment cognitive-linguistic measures (random effects), and participant-specific factors (random effects) explain post-treatment naming and connected speech outcomes. We will calculate effect sizes by subtracting a participant's average pre-treatment score from their average post-treatment score and dividing by the pre-treatment standard deviation⁸.

Aim 1a. Measure PWAs' naming accuracy for trained and untrained objects. We will calculate effect sizes to measure the effect of treatment on participants' naming accuracy for trained objects, untrained semantically-related objects, and untrained semantically-unrelated objects between pre- and post-treatment. Hypotheses: Consistent with prior studies, we expect that naming treatment will yield medium to large effects for trained objects. Additionally, we hypothesize that strategy training will result in an increase in circumlocution-facilitated naming for untrained unrelated objects and yield medium effects for all untrained objects, regardless of semantic relatedness.

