d. Power analysis (sample size, evaluable subjects). We will recruit 20 PWA subsequent to single left-hemisphere stroke with the goal of collecting complete data on ten participants, which is adequate for single-subject design^{68,69}.

VII. RISKS AND DISCOMFORTS

a. Complications of surgical and non-surgical procedures. Language and cognitive assessments and therapy tasks are noninvasive and pose no medical risks. Participants may experience some frustration during the course of the study, however, this frustration is not expected to be more than that what would be faced in situations requiring focused, sustained

attention for learning. A researcher will be present to answer any questions or concerns participants might experience.

All materials (history forms, data obtained during behavioral tasks) are for research purposes only and will be kept in confidence. Forms containing personally identifying information (history forms and data collected during cognitive-linguistic assessments) will be kept in a locked filing cabinet at the MGH IHP to which only the PI and approved study staff have access.

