In-person sessions will occur in The Aphasia Center at [name], or in guiet rooms in building 79/96 the MGH IHP's research building. Rooms are equipped with wall-mounted cameras (Eagle 1.3 Megapixel camera), which will be used to video/audio recording assessment and treatment sessions. For in-person and at-home sessions, video/audio recordings will be collected using password-protected Enterprise Zoom on an encrypted, password protected laptop. For virtual sessions, video/audio recordings will be collected using password-protected Enterprise Zoom, and study staff will launch the video conferencing in a private and secure area. All digital data (i.e., video/audio recordings) will be transferred to a secure network or webbased electronic lab notebook, LabArchives, and/or Dropbox, maintained by Partners, which can only be accessed by the PI and approved study staff via electronic ID. These digital files will be coded with identification codes and will not contain personally identifiable information. Deidentified standardized assessment scores will be transferred from paper forms to digital forms in RedCap. Video data will be recorded and kept on a secure network maintained by Partners and accessed only by approved researchers. Deidentified video clips will be kept for education purposes (teaching within MGB only). If we do utilize videos, participant faces will be blurred/obscured as to remain de-identified. Video and audio recordings will be retained for seven years and then be destroyed.

- b. Drug side effects and toxicities: N/A
- c. Device complications: N/A
- d. Psychosocial (non-medical) risks: N/A
- e. Radiation Risks: N/A

VIII. POTENTIAL BENEFITS

- **a.** Potential benefits to participating individuals. It is hoped that the treatment will result in behavioral gains for around 80% of enrolled subjects, as demonstrated through improved performance on naming batteries and cognitive-linguistic assessments administered post-treatment.

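### Statements across participants would describe only those who reach post-treatment testing: the 20-to-10 gap is not split into screen failure and dropout, and stopping treatment is not separated from leaving the study

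*Combined protocol and SAP*

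**What the plan says.** All references are to the combined protocol and SAP.

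- **Numbers.** Section IV.a: "We plan to enroll 20 individuals with aphasia in a single-subject design intervention study". Section VI.d recruits the same 20 "with the goal of collecting complete data on ten participants, which is adequate for single-subject design". It does not define complete data, give a dropout rate or explain the difference.
- **Screening after consent.** Section III.a sets a minimum comprehension score and a naming range of 1 to 146 of the 176 items. It says of these: "These criteria will be assessed at the initial study visit, after informed consent has been obtained". Passing is needed "for full enrollment/participation in the study. Individuals who name 0, or greater than 146 items will be excluded".
- **Leaving.** Section VI.b: "The participant's participation with the study will end when they request to withdraw from the study", or once the post-treatment assessments are done. No other exit is described for a person who gives up treatment before its planned end.
- **Outcome.** Section VI.c computes each effect size by "subtracting a participant's average pre-treatment score from their average post-treatment score and dividing by the pre-treatment standard deviation". The normalized change scores and the change in WAB-R Aphasia Quotient also compare before with after, and the mixed models are meant to explain post-treatment outcomes.
- **Hoped-for benefit.** Section VIII.a: "It is hoped that the treatment will result in behavioral gains for around 80% of enrolled subjects", as shown on assessments given after treatment.

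**The concern.** A plan that aims for complete data on half its recruits needs to say what happens to the other half. Treatment runs to as many as 3 × 8 = 24 sessions of 70 minutes, and Section VII.a accepts that some participants may be frustrated. It is plausible, though not shown, that those who gain least are likelier to stop. Re-assessment falls 20 to 30 days after the last treatment session, so anyone who has withdrawn by then has no post-treatment score. That person drops out of the effect sizes, the change scores and the models of post-treatment outcome.

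At stake is what the study can say about the group: whether effects are typically medium to large, what predicts them, and what share of people gain. If loss is related to outcome, those statements would look better than the experience of everyone who began treatment. The hoped-for 80% adds a second difficulty, because its denominator is the number enrolled and the plan does not fix what that number is.

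**Working it through.** **1. The plan's own figure.** There is no power calculation to reproduce: no alpha, power, target effect or standard deviation is given. The only check is to back-solve the loss: 1 − 10/20 = 0.50, and 10/(1 − 0.50) = 20. This is circular, since the 50% comes from the same two numbers. It confirms nothing about dropout.

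**2. Who can have an effect size.** The formula is (mean post − mean pre) / pre-treatment SD, for each participant. With no post-treatment score it cannot be computed. With at least one it can, even if a weekly probe or retention visit was missed. The group with effect sizes is therefore those with post-treatment data, which may be larger than the group with complete data.

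**3. The 80% statement.** Let E be the number counted as enrolled, and suppose ten people have post-treatment data. The largest share that can demonstrate a gain is 10/E. The number of people needed is 0.80 × E, rounded up.

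| E | Recruits not counted as enrolled (20 − E) | Needed for 80% | Largest demonstrable share (10/E) |
|---|---|---|---|
| 10 | 10 | 8 | 100% |
| 12 | 8 | 10 | 83% |
| 13 | 7 | 11 | 77% |
| 15 | 5 | 12 | 67% |
| 20 | 0 | 16 | 50% |

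The crossing point is 10/0.80 = 12.5. With ten assessed, the hoped-for share can be shown for E of 10 to 12 and cannot for E of 13 to 20.

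**4. What ten assessed people say about 20.** Suppose all 20 start treatment, ten are assessed, eight of those gain, and a fraction q of the other ten would have gained. The share among all 20 is (8 + 10q)/20:

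- q = 0 gives 40%.
- q = 0.4 gives 60%.
- q = 0.8 gives 80%.
- q = 1 gives 90%.

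It equals 80% only if those not assessed gain at the same rate as those assessed. Sampling error is separate: for 8 of 10 the exact 95% interval is 44% to 97%.

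The split of eight of ten, the count of ten assessed and the values of q are assumptions chosen to show the range. None is a forecast in the documents.

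**The case against.** The case on the other side is substantial, and much of it stands.

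- **Enrolled may not mean 20.** Section III.a ties full enrollment to passing a screen held after consent. Up to ten of the 20 could be screen failures, who are not dropouts. Section IV.a nevertheless uses enroll for all 20, so the term is ambiguous. A reader might infer that the 80% is impossible on the plan's own numbers; the documents support that only for some meanings of enrolled.
- **Ten is a goal, not a cap.** Data can be incomplete for reasons other than dropout, such as a missed retention visit. Section IV.b also lets people take part without being recorded, while Section V.e has naming coded from audio. More than ten could have effect sizes.
- **The 80% is a hope** under Potential Benefits. It is not an endpoint, a success criterion or an input to the sample size. The mismatch is one of wording.
- **Individual effect sizes are not biased by others leaving**, and no group average of them is specified. This stands. The hypotheses, the mixed models and the share who gain remain statements across participants.
- **Data before withdrawal are not said to be discarded.** Visual inspection is planned for all results, so a partial participant's weekly data still have a use. Those probes cover a selected list of objects, however, and do not replace the 176-item assessment.

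A reader might also turn the 50% gap into a bias of definite size. The documents do not support this. They give no dropout rate, no reasons for loss and no relation between loss and gain, and the gap may be partly screening.

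**Conclusion.** The point holds in a limited form. Conclusions across participants would rest on those who reach post-treatment testing, because every effect size and change score needs a post-treatment score and the only stated early exit is withdrawal, which ends participation. If dropout is related to outcome, those conclusions could overstate benefit. The direction is plausible, but the size cannot be derived from the documents. Individual effect sizes are not affected.

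On the 80%, the conclusion is conditional. If enrolled means 20 and only ten are assessed, 16 of 20 could not be demonstrated. If 12 or fewer pass the post-consent screen and ten are assessed, there is no conflict. The documents do not settle which applies. None of this invalidates the single-subject design; it is a gap in follow-up and reporting that can be closed cheaply.

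**What to change.** - **Section VI.b.** Separate stopping treatment from withdrawing from the study. Offer the already planned post-treatment naming assessment to anyone who stops treatment but agrees to be seen.
- **Section VI.c.** Base across-participant summaries on everyone who starts treatment. Report how many lack post-treatment data, and why. Show those people's weekly probe data descriptively, through the visual inspection already planned, and not as a substitute for the 176-item outcome.
- **Sections VI.d and VIII.a.** Report post-consent screen failures separately from dropout. Express the hoped-for share with gains as a proportion of those who start treatment.

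The cost is one existing assessment offered to a few people, some wording, and a benefit figure that may be less favourable.
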